1.1 Background and rationale

Attention deficit hyperactivity disorder (ADHD) is one of the most common neurodevelopmental disorders among school-aged children. The prevalence in China is estimated to be 6.26%[1]. ADHD is characterized by age-inappropriate inattention and/or hyperactivity-impulsivity[2]. ADHD marks a significant risk for later development of the oppositional defiant disorder, conduct disorder, and more serious antisocial behavior in adolescence, impairs academic achievement and social function, which may lead to impaired relationships with family and peers, self-esteem, and quality of life[3].

Treatment for ADHD is typically recommended as multimodal approaches, which usually include medication and behavioral interventions as first-line treatment[4]. Stimulant and non-stimulant medications are the most efficacious treatments for inattentive and hyperactive/impulsive symptoms. However, parents' side effects and concerns have limited medication use in many patients[5]. Non-pharmaceutical behavioral interventions mainly consist of parent training in behavior management and behavioral classroom interventions. Behavioral interventions are shown to improve social and behavioral outcomes. Still, it is not as effective as medication in reducing the core symptoms of ADHD. It is usually quite time and labor-consuming and costly, making it challenging to implement in developing countries like China[6,7].

Given these findings, physical exercise is indicated as an alternative approach to the treatment of ADHD. It is proposed by many researchers to be used independently or complementary to medication or behavioral interventions to attenuate the adverse effects of ADHD. Physical exercise improves cognition, fitness, physical function, mood, and behaviors in household and school settings in children with ADHD[8–12]. Several studies also highlighted the efficacy of physical exercise in the reduction of core symptoms of ADHD[8,9,12–16]. Furthermore, physical exercise interventions can yield acute and lasting positive effects on executive function (EF), known as the core neurobiological deficit in ADHD[17]. This neural rehabilitating effect is shown by improvements in processing speed, working memory, planning, and inhibitory control after physical exercise[13,18–21]. The underlying mechanism may be associated with the increased levels of synaptic proteins, glutamate receptors, norepinephrine and dopamine levels, and the availability of brain-derived neurotrophic factor (BDNF) and insulin-like growth factor-1 generated by physical exercise, all of which can promote neural plasticity leading to the adaptive biological response of brain function[22–26].

Physical exercise, including tai chi chuan and Baduanjin, is also seen as an essential alternative approach in Traditional Chinese Medicine (TCM). In the theory of TCM, the pathogenesis of ADHD is the imbalance of yin-yang and dysfunction of the Zang-fu (viscera) organs[27]. The TCM treatment of ADHD is individualized, mainly composed of Chinese herbal medicine, adjuvant acupuncture, tui na, diet, and physical exercise [28,29]. The Eight-brocade Exercise (Baduanjin) is an ancient Chinese qigong physical exercise that likely originated more than one thousand years ago. Baduanjin exercise comprises 8 sets of gentle, elastic, and integrated mind-body movements; each group targets a specific organ or health need, which can be easily administered to children

and adolescents. Baduanjin has already been proven to improve the physical function of primary school students, including physical coordination, abdominal strength, and flexibility[30]. Researchers have also demonstrated that Baduanjin has a protective effect on cognitive functions such as selective attention in patients with mild cognitive impairment. The result is significantly larger than the brisk walking group[31]. The score of the Schulte grid scale was also considerably improved after 12 weeks of daily practice of Baduanjin in another research, which showed its potential for attention improvement[32].

Given the above backgrounds, investigators will evaluate the effectiveness of Baduanjin exercise compared to routine physical exercise and its underlying mechanism in a randomized controlled trial.

1.2 Objectives

This randomized controlled trial aims to compare the efficacy of Baduanjin exercise to routine physical exercise in ADHD patients with Hyperactive-Impulsive Symptoms after three months of exercise and evaluate whether this effect will last for another three months.

The primary objective is to compare the Hyperactivity/Impulsivity change scores between two groups of The Swanson, Nolan, and Pelham Questionnaire (SNAP-IV) Rating Scale in 3th and 6th months after initiation. The secondary objective of this study is to evaluate the change in Scoring evaluation of the TCM symptoms after 3 months of treatment and 6 months of follow-up. In addition, the mediating effect of executive function measured by the CANTAB test and BRIEF2 scale will be calculated. Furthermore, we will determine whether these effects extend to other ADHD-related problems, including the sensory integration score, the Developmental Test of Visual Perception, and other behavioral problems.

1.3 Trial design

This is a single-center, single-blind, superiority, randomized controlled trial. This study is planned to be conducted from October 2020 to March 2022 at the Children's Hospital of Fudan University. Patients will be recruited at the child psychology clinic and TCM clinic of the Children's Hospital of Fudan University. Each participant who fulfills the eligibility criteria outlined in the protocol is randomly allocated consecutively to either the Baduanjin exercise group or the general physical exercise group with a ratio of 1:1.

2 Methods: Participants, interventions, and outcomes

2.1 Study setting

This trial is being performed in the Children's Hospital of Fudan University, which is a comprehensive tertiary pediatric hospital and one of the national children's medical centers. Patients are enlisted at the clinic of both the Child psychology department and TCM department.

2.2 Eligibility criteria

Patients are considered for inclusion if they meet the criteria as defined below.

2.2.1 Inclusion Criteria

Inclusion criteria: (1) Age between 7 years 0 months to 16 years 11 months. (2) Diagnosed with ADHD at the clinic of the Child psychology department, with Combined Presentation or Predominantly Hyperactive-Impulsive Presentation. (3) Doctor version of SNAP-IV Hyperactivity/Impulsivity score ≥ 12 . (4) Full-Scale Intelligence Quotient ≥ 80 (Wechsler intelligence scale for children-IV). (5) Resident in Shanghai, Zhejiang province, and Jiangsu province. (6) The parents or caregivers can understand the content of the study, are willing to participate in the follow-up visits, and complete the required information.

2.2.2 Exclusion Criteria

Exclusion criteria: (1) Currently using psychiatric medication other than methylphenidate as the treatment plan at the time of enrollment and planning to use it within the upcoming three months. (2) Comorbid with the epileptic disorder, attack stage of child asthma, or other existing physical illness that makes the routine physical exercise risky to the patient. (3) Comorbid with Tourette syndrome, Autism Spectrum Disorder, Learning disorder, Mood disorder, Psychotic disorder, or under suicidal risk. (4) Attending other regular athletic training under professional guidance during the intervention period. The gym class and after-class sports activities at school are not considered professional-guided athletic training. (5) Receiving regular psychological treatment or attending any other clinical research during the intervention.

2.3 Who will take informed consent?

This trial's information is posted in our clinic's hallway and introduced to all the families. All the families receiving this information are welcome to sign up for the trial by completing a simple electric application form on their mobile phones. We will screen their application to assess their eligibility and call the parent to provide initial study information and answer their questions. After this discussion, the family intent to participate in the study will be scheduled to meet with the research physician to discuss any remaining questions, finish the inclusion evaluation and sign in the informed consent. Written informed consent is obtained from the legal guardian of each participant before they undergo any interventions related to the study. Researchers will also explain the trial details explicitly to participants over eight years old and obtain their signed consent.

2.4 Interventions

2.4.1 Explanation for the choice of comparators

Many cross-sectional studies support a positive relationship between routine physical activity and executive function development, decreased behavioral problems, and impulsivity control in children with ADHD. We assumed that Baduanjin exercise is superior to other routine physical exercises. Therefore, the control group is guided to take any routine physical exercise, including jogging, bike-riding, badminton, table tennis, soccer, basketball, aerobics, and rope skipping for 30 minutes, five days each week, under the supervision of caregivers. The caregivers are trained during inclusion interviews by the physician to understand the idea of aerobic physical exercise and the technique to help their child choose their favorite sports activity and make it a daily routine. Each child participating in this trial is given a Huawei fitness tracker with a heart monitor, which is used to monitor the body information during their daily exercise. Researchers will check the uploaded data of the fitness tracker on a daily basis. The time of exercise is required to exceed 30 minutes each time, and the maximum heart rate during the exercise should be over 120 beats per minute. This is the comparator of choice for the Baduanjin exercise in this study.

2.4.2 Intervention description

The Baduanjin exercise group is asked to use the Baduanjin training system to practice the whole set of Baduanjin at least once a day and at least 5 days each week for 3 months. The Baduanjin training system is a video game designed with motion tracking and motion recognition strategy by the research team, providing a motivating full-body interactive experience for children with ADHD to engage in practice. Caregivers included in the Baduanjin intervention group were equipped with a Kinect sensor bar, connector, and software package on the day of enrolment. The software and electronic equipment installation is guided by researchers on the same day in the

hospital and at their homes later if necessary.

During the study, the children were asked to practice Baduanjin using the given software for at least 30 minutes daily, 5 times each week. They can practice any single brocade or the whole combination of 8 movements using the different game modes in the software. Instructions for movements and the variety of breath are provided in each game mode. The eight movements of Baduanjin are listed as follows:

1. Hold up the hands to regulate the triple burner;
2. Draw a bow like shooting a hawk;
3. Raise one arm to regulate the spleen and stomach;
4. Turn the head back to treat consumptive diseases and injuries;
5. Sway the head and swing the buttocks to expel the heart-fire;
6. Hold the feet by the hands to reinforce the loins and kidneys;
7. Punch with anger;
8. Hold and drop the heels to improve the health of the spine.

During their exercise, the child's motion will be captured and projected onto the screen, and their movement will be scored according to accuracy. The advice on motion adjustment is given immediately, and the feedback of data will be shown on the screen after each round of the game, then uploaded to a management website to be monitored by researchers.

The children in the Baduanjin group were asked to use the fitness tracker and uploaded data the same as the control group. The time of exercise is required to exceed 30 minutes each time, and the maximum heart rate during the exercise should be over 120 beats per minute. Researchers will also check with the data uploaded automatically by the Baduanjin software to ensure the movements are adequately practiced.

2.5 Criteria for discontinuing interventions

Participants can leave the trial at any time for any reason without any consequences if they request to do so. If they decide to leave before the intervention starts, the patient will be replaced by the following new patient. During the intervention, the drop-out is defined as the following: changing the dose of methylphenidate and or receiving another behavioral intervention according to the advice of an independent child psychiatrist, stopping taking exercise for two consecutive weeks without a reasonable cause, and/or the refusal to attend both study visits at 3 months \pm 4 weeks and 6 months \pm 4 weeks after allocation. Advises about preventing sports injury are talked about with caregivers at the enrollment. In case of a sports injury or illness for other reasons, the caregivers are asked to contact the primary investigator to discuss whether to pause the exercise or end it. The patient data will be recorded up to the drop-out and included in the analysis.

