2.7 Participant timeline

Outcome measures are collected at enrolment, 3 months allocation, and 6 months post allocation. The flow of the trial is presented in Figure 1. A schematic diagram of enrolment, interventions, and assessments is described in Table 1.

TG: treatment group, CG: control group, SNAP-IV: The Swanson, Nolan, and Pelham Questionnaire

Figure 1 Flow diagram showing study design and subject allocation

Table 1 Enrolment, interventions, and assessments

| | STUDY PERIOD | | | |
|-------------|--------------|------------|-----------------|-----------|
| | Enrolment | Allocation | Post-allocation | Close-out |
| TIMEPOINT** | -2 Weeks | 0 | 3 months | 6 months |
| ENROLMENT: | | | | |

| | | | | |
|--|---|---|---|---|
| Eligibility screen | ✓ | | | |
| Informed consent | ✓ | | | |
| Allocation | | ✓ | | |
| INTERVENTIONS: | | | | |
| Baduanjin practice | ✓ | ✓ | ✓ | ✓ |
| routine physical exercise | ✓ | ✓ | ✓ | ✓ |
| ASSESSMENTS: | | | | |
| Primary Outcome: SNAP-IV clinician-rated Hyperactivity/Impulsivity score | ✓ | | ✓ | ✓ |
| Secondary Outcome: Scoring evaluation of the TCM symptoms(researcher rated) | ✓ | | ✓ | ✓ |
| Other outcome measures: | | | | |
| SNAP-IV parent/clinician-rated inattention and ODD score | ✓ | | ✓ | ✓ |
| WFIRS (parent completed) | ✓ | | ✓ | ✓ |
| CBCL (parent completed) | ✓ | | ✓ | ✓ |
| SDQ(parent and child completed) | ✓ | | ✓ | ✓ |
| CANTAB(child completed) | ✓ | | ✓ | ✓ |
| BRIEF-2 (parent completed) | ✓ | | ✓ | ✓ |
| DTVP-2(child completed) | ✓ | | ✓ | ✓ |
| Child Sensory Integration Checklist (parent completed) | ✓ | | ✓ | ✓ |

SNAP-IV: The Swanson, Nolan, and Pelham Questionnaire; TCM: Traditional Chinese Medicine; ODD: Oppositional Defiant Disorder; WFIRS: Weiss Functional Impairment Rating Scale; CBCL: Achenbach Child Behavior Checklist; SDQ: Strengths and Difficulties Questionnaire; CANTAB:

Cambridge neuropsychological test automated battery; BRIEF-2: Behavior Rating Inventory of Executive Function, Second Edition; DTVP-2: Visual Perception of children is measured by the Developmental Test of Visual Perception-2nd edition.

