2.10.2 Concealment mechanism

The statistician will conceal the allocation sequence and place it sequentially numbered, opaque, sealed, and stapled envelopes. After signing the informed consent from parents, the study investigators will open the envelopes in consecutive orders and randomly assign the subjects to the intervention group or the control group according to the allocation scheme in the envelope.

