2.10.3 Implementation

The statistical department of our hospital generates the allocation sequence. The researchers will use the prepared sealed envelopes to allocate the patient to a study arm and finish the enrollment procedures. The study group will be revealed, and intervention will be introduced after allocation to the participants.

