## 3.4. Randomization

According to the random seeds (seed:20200618), numbers from 1 to 6 were randomly generated by the R software (version 4.0.0) for each block, and each number corresponded to one of six plans for allocating four participants of the block to two arms in a 1:1 ratio. Each allocation sequence was placed in small, opaque, and sealed envelopes numbered and marked in order from one to four and were enclosed in a larger,

opaque, and sealed envelope marked with the block number.

A randomization plan and concealed envelopes were prepared by an independent team of statisticians from the Clinical Trial Unit (CTU) of the Children's Hospital of Fudan University. Recruited patients will be randomly allocated in a 1:1 ratio to the control or experimental group based on the randomization plan: After obtaining signed informed consent from the eligible participant, the trained physician will meet with the prespecified institutional nurse to achieve the allocation plan for the very participant, as indicated by the corresponding envelope. Block envelopes and the four enclosed small envelopes will be opened in order. The nurse will administer the allocation record form in front of the physician.

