#### *-Intent-to-Treat population*

Intent-to-treat (ITT) population will be defined at the moment the randomization is performed. This will be the primary analysis for the trial.

Participants will be excluded from the ITT analysis if the primary outcome is missing, forming a modified ITT population (mITT).

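### Protocol 2.5 does not limit replacement to children who leave before allocation, so it can reach a randomised child whose family knows the arm, and this is not reconciled with the SAP's ITT population

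*Protocol*

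**What the plan says.** Protocol 2.5 gives the replacement rule in one sentence: "If they decide to leave before the intervention starts, the patient will be replaced by the following new patient". It mentions neither allocation nor the envelope. The same section defines drop-out only for events during the intervention, and it promises to analyse data recorded up to drop-out.

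On the order of events, Protocol 2.10.2 says "After signing the informed consent from parents, the study investigators will open the envelopes in consecutive orders", and Protocol 2.10.3 says "The study group will be revealed, and intervention will be introduced after allocation to the participants". Table 1 in Protocol 2.7 puts consent at week -2 and allocation at time 0. In the Baduanjin arm, equipment is set up on the day of enrolment in the "hospital and at their homes later if necessary" (Protocol 2.4.2).

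On the sequence, SAP 3.4 says "Block envelopes and the four enclosed small envelopes will be opened in order".

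On the analysis sets, SAP 4.2 says "Intent-to-treat (ITT) population will be defined at the moment the randomization is performed". It then removes children whose primary outcome is missing, which gives the modified ITT (mITT) set. SAP 5.1.1 bases the primary analysis on that set. The SAP does not mention replacement.

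**The concern.** A replacement rule does no harm as long as nobody knows the child's arm. After disclosure, the decision to leave can depend on the arm. Families here are not blinded, and the offers differ visibly: one arm receives a motion-tracking video game, the other is asked to do ordinary sport. Refusal that differs by arm is plausible.

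If such a family is handled as replaced, two things follow. The recruitment total is refilled, so there is less reason to pursue the leaver. And no passage asks that child back for the 3-month rating, so the mITT rule removes the child from the primary analysis. The two arms being compared could then differ in who agreed to start, not only in what they did. At stake is the primary comparison, the 3-month change in the clinician-rated Hyperactivity/Impulsivity score.

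**Working it through.** **1. Where the rule bites.** Set the steps in order:

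- Consent (week -2) to envelope opening (time 0): a leaver has no arm. Replacement is harmless.
- Envelope opened and arm disclosed, to first exercise: a leaver has been randomised and knows the arm. Protocol 2.5 still permits replacement. SAP 4.2 already counts this child in the ITT population.
- After first exercise: Protocol 2.5 no longer permits replacement.

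Only the middle interval is a problem. Neither document gives its length or defines when the intervention starts.

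**2. The plan's own sample size.** Inputs from SAP 3.6: difference 3.1, SD 5.8, 80% power, two-sided alpha 0.05.

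- Normal approximation: n = 2 × (1.960 + 0.842)² × 5.8² / 3.1² = 54.95, so 55 per arm.
- Two-sample t-test: 55.93, so 56 per arm, as stated.
- 5% drop-out: 56 / 0.95 = 58.9, so 59 per arm or 118 in total. The plan has 120.

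The plan's figure reproduces.

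**3. Possible shift in the primary difference.** The documents give neither the number leaving after allocation nor their prognosis. Assume that all leavers come from one arm, make up a share f of it, and would have had a mean change d SDs away from the stayers. Then shift = f × d × 5.8 points.

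| Share of one arm | 0.25 SD | 0.5 SD | 1 SD |
|---|---|---|---|
| 2% | 0.03 | 0.06 | 0.12 |
| 5% | 0.07 | 0.15 | 0.29 |
| 10% | 0.15 | 0.29 | 0.58 |
| 15% | 0.22 | 0.44 | 0.87 |

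As a fraction of 3.1 points, the range is about 1% (0.029/3.1) to 28% (0.87/3.1). If leaving is non-selective, the shift is zero.

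**4. What causes the shift.** Take 60 in an arm, 6 leavers, and stayers with mean m.

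- All 60 observed, leavers differing by 5.8: (54m + 6(m − 5.8)) / 60 = m − 0.58.
- Leavers unrated, no replacement: mean of 54 stayers = m.
- Leavers unrated, 6 replacements resembling stayers: (54m + 6m) / 60 = m.

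The last two are equal. The 0.58 points come from the missing outcomes of the leavers; replacement adds nothing to it.

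**5. Power if post-allocation leavers are not replaced.** Two-sample t-test, difference 3.1, SD 5.8, 60 randomised per arm:

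| Lost per arm | Analysed per arm | Power |
|---|---|---|
| 0 | 60 | 82.7% |
| 3 (5%) | 57 | 80.8% |
| 5 | 55 | 79.3% |
| 6 (10%) | 54 | 78.6% |
| 12 (20%) | 48 | 73.6% |

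**The case against.** The best case for the plan is that Protocol 2.5 is a recruitment rule and not an analysis rule. It never says that an allocated child is replaced, and its wording also fits the two weeks between consent and allocation, where replacement is proper. The interval after disclosure may be short, since equipment is set up on the day of enrolment and home visits happen only if needed. SAP 4.2 would formally keep an allocated leaver in the ITT population. It is the mITT rule that removes the child, whether or not a replacement is recruited. All of this stands, and step 4 confirms the last part. It does not close the gap: nothing confines the rule to the harmless interval, and nothing says how an allocated leaver is followed up or analysed.

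Three stronger readings are tempting, and the documents do not support them.

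- *Randomisation is broken.* Both documents have the envelopes opened in sequence, which points to the next envelope for the next child. No passage says that a newcomer inherits a vacated slot. If one did, that child's arm would be known before enrolment, but this is a possibility left unaddressed and not a stated procedure.
- *The harms denominator is biased.* The safety population in SAP 4.2 consists of children given some exercise-related treatment. A child who leaves before exercise starts is outside it in any case.
- *The bias favours Baduanjin.* The direction is unknown. Losing control children with poorer outcomes would improve the control mean and work against Baduanjin; losing such children from the Baduanjin arm would do the opposite.

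**Conclusion.** The point holds as a gap between the two documents. Protocol 2.5 sets the replacement cut-off at the start of exercise, the arm is known before then, and the result is not reconciled with an ITT population fixed at randomisation. An allocated leaver who is treated as replaced has no stated follow-up and would drop out of the mITT primary analysis.

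The consequence is a risk of selective loss after randomisation, not a demonstrated bias. Its size cannot be computed from the documents. The range of 0.03 to 0.87 points rests on three assumptions: leavers in one arm only, 2% to 15% of that arm, and a difference of 0.25 to 1 SD. A reader might take that range as the harm done by replacement itself. It is not; it is the effect of not having the leavers' outcomes. Banning replacement without seeking those outcomes would therefore recover none of it.

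**What to change.** Change Protocol 2.5 so that:

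- a family may be replaced only if it leaves before the allocation envelope is opened;
- once the envelope is opened, the child is not replaced, and the envelope or slot is never reassigned;
- that child counts as randomised in the allocated arm, and the family is asked to attend the 3- and 6-month ratings even if exercise never starts.

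In the SAP, report by arm the number leaving between allocation and first exercise. Add a sensitivity analysis of the primary outcome that includes all randomised children under stated assumptions about the missing outcomes, with those assumptions allowed to differ by arm. Protocol 2.5 and 2.10.3 and SAP 4.2 and 5.1.1 should then agree.

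The required sample size does not change. The cost is that a few allocated children are not made up: power is 80.8% with 3 lost per arm and 78.6% with 6. Early leavers would share the 5% allowance with later drop-outs, so it covers only a few of them. If enrolment has already closed (Protocol 1.3 planned the study to March 2022), the amendment comes too late to change recruitment. Every opened envelope can still be accounted for by arm, and the sensitivity analysis can still be added.

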2.5.3 Relevant concomitant care permitted or prohibited during the trial

Both groups receive standard care in the clinic during the intervention. Additional sensory integration therapy and child behavioral group or individual therapy are permitted once they complete the 3-months follow-up.

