2.12 Data collection and management

2.12.1 Plans for assessment and collection of outcomes

The outcomes will be collected at 3 months and 6 months after allocation. Considering the ongoing COVID-19 quarantine, we allow participants to finish the first outcome evaluation at 3 months \pm 4 weeks, and for the second outcome evaluation, 6 months \pm 4 weeks.

The research staff is required to receive a three-hour training session to ensure that they fully understand the protocol and standard procedures for the trial. The blinded physicians for evaluating the primary and secondary outcomes attend a one-hour training on the outcome assessment. All the research questionnaires and tests will be conducted at the Children's Hospital of Fudan University. Data will be collected with a case report form (CRF) and recorded in an ACCESS database. The description of study instruments is provided in the outcome part of this protocol. The demographic information of participants, including birth date, sex, height, weight, routine habit of exercise, and current drug use, are recorded on the CRF. The test record of CANTAB will be downloaded from the Cambridge cognition official website and automatically saved as an excel document. All data collected during the study will be kept in a locked room or protected research server. Back-ups in the study folder on this protected research server will be saved regularly (once per 3 months). Only the study team has access to these documents. To ensure this trial is applied consistently to high quality, the Clinical Trial Unit (CTU) of Children's Hospital of Fudan University will regularly monitor enrolment records, CRFs, informed consent, and data records.

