2.15 Statistical methods

2.15.1 Statistical methods for primary and secondary outcomes

The primary outcome is a continuous variable: Hyperactivity/Impulsivity score change in the SNAP-IV scale. The primary analysis will be based on the intention-to-treat (ITT) population. The generalized linear model (GLM) will be used to test the difference 3 months after allocation between the groups. The estimated means and two-sided 95% confidence intervals (CI) will be derived. All secondary outcomes will be analyzed for a superiority-designed trial and two-sided significance with alpha=5% and standard 95% CIs for the treatment differences in these outcomes between the two treatment groups. Secondary outcome analyses will be based on the ITT population unless specified. SAS (version 9.4) will be used to perform all data analyses and generate the majority of data displays. STATA® (version 16.0) or SPSS, S-Plus, or R may also be used for data analyses and for generating statistical graphs. The other outcome measures will be calculated and presented with the same method of primary and secondary outcomes. Continuous variables will be summarized according to the number of subjects with non-missing data (n), mean, standard deviation (SD), median, minimum, maximum, and range interquartile (IQR). The confidence intervals will be reported on summaries of continuous effectiveness variables. Categorical variables will be summarized according to the absolute frequency and percentage of subjects (%) in each category level. The denominator for the percentages is the number of subjects in the treatment arm with data available unless noted otherwise.

Detailed information is displayed in the SAP.

2.15.2 Plans to give access to the complete protocol, participant-level data, and statistical code

The datasets used and analyzed during this trial can be granted access by the corresponding author and the safety monitoring board(DSMB) of CTU upon reasonable written request.

3 Oversight and monitoring

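### Protocol 2.5 stops data recording at 'drop-out', a term that includes treatment changes; followed as written, such a child has no 3-month score and leaves the primary analysis

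*Protocol*

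**What the plan says.** Protocol 2.5 gives one definition of drop-out during the intervention. It covers three kinds of event:

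- a change in treatment: "changing the dose of methylphenidate and or receiving another behavioral intervention according to the advice of an independent child psychiatrist";
- a stop in exercise: "stopping taking exercise for two consecutive weeks without a reasonable cause";
- a refusal of follow-up: "the refusal to attend both study visits" (the 3-month and the 6-month visit).

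One data rule follows for all three: "The patient data will be recorded up to the drop-out and included in the analysis".

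The visit schedule carries no conditions. Protocol 2.7 states: "Outcome measures are collected at enrolment, 3 months allocation, and 6 months post allocation". Protocol 2.12.1 states: "The outcomes will be collected at 3 months and 6 months after allocation", each with a window of 4 weeks either side. No clinician rating falls between baseline and month 3.

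On the analysis set, Protocol 2.15.1 states: "The primary analysis will be based on the intention-to-treat (ITT) population". SAP 4.2 defines ITT at randomisation but removes participants whose primary outcome is missing, which gives the mITT set. SAP 5.1.1 runs the primary mixed model on that set. SAP 5.2.1 imputes baseline covariates only.

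The definition concerns the intervention period. For the time after it, Protocol 2.5.3 states: "Additional sensory integration therapy and child behavioral group or individual therapy are permitted once they complete the 3-months follow-up".

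**The concern.** Stopping or changing a treatment is not the same as leaving follow-up. A child whose methylphenidate dose is changed in week 6 can still be rated at month 3, and an ITT comparison needs that rating. Protocol 2.5 puts both events under one label and ends recording at the label.

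A dose change or an added therapy on a psychiatrist's advice may be related to how the symptoms are going. Children with such events may therefore differ from the rest, and the two arms need not lose the same kind of child. If they are left out, the primary comparison is made between groups that randomisation no longer protects. A rating not taken within its window cannot be obtained later, so the analysis cannot repair the gap.

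**Working it through.** **Logic of the text**

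1. A treatment event occurs before month 3. Under Protocol 2.5 the child is a drop-out.
2. Data are recorded up to that point. The last clinician rating is the baseline one (Protocol 2.7, 2.12.1).
3. The primary outcome is the 3-month score minus baseline (Protocol 2.6.1, SAP 2.2.1), so it is missing.
4. SAP 4.2 removes the child, and SAP 5.1.1 analyses those who remain. A maximum-likelihood mixed model can use partial data, but the exclusion comes first.
5. Protocol 2.5 says such data are to be included in the analysis and Protocol 2.15.1 names ITT. For this child neither is met.

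If the child is nevertheless rated at month 3, the primary outcome is not missing, and SAP 4.2 and 5.1.1 include the score.

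**Inputs** (SAP 3.6; 1:1 ratio from Protocol 2.10.1): difference 3.1, SD 5.8, two-sided alpha 0.05, power 80%, 56 per arm, 5% drop-out, 120 randomised.

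**The plan's own figure.** A two-sample t-test with these inputs needs 55.93 per arm, so 56. Allowing for 5% drop-out, 112 / 0.95 = 117.9, so 118. The stated 120 is consistent with this and is a multiple of the block size of 4. The sample size reproduces.

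**Margin for missing 3-month scores, all causes.** 120 / 2 = 60 per arm; 60 − 56 = 4 per arm; 8 / 120 = 6.7%. The planned 5% is 0.05 × 120 = 6 children.

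**Power if children are left out.** The t-test has 2n − 2 degrees of freedom and noncentrality (3.1 / 5.8) × √(n/2). At n = 60 this is 0.5345 × 5.477 = 2.93.

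| Scored per arm | Missing per arm | Power for 3.1 points |
|---|---|---|
| 60 | 0 | 82.7% |
| 57 | 3 (5%) | 80.8% |
| 56 | 4 | 80.1% |
| 55 | 5 | 79.3% |
| 54 | 6 (10%) | 78.6% |

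**Dilution if all 60 per arm are kept.** Assume that a share d of children gain nothing from Baduanjin over control and the rest differ by 3.1. The difference is then 3.1 × (1 − d). The documents do not give d.

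| d (assumed) | Difference | Power, 60 per arm |
|---|---|---|
| 0% | 3.10 | 82.7% |
| 5% | 2.95 | 78.8% |
| 10% | 2.79 | 74.3% |
| 20% | 2.48 | 64.2% |

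The 78.6% in the first table and the 74.3% in the second do not compete. The first is power for the difference among the children who remain. The second is power for the difference among all who were randomised.

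**The case against.** The best counter-argument is that the rule was not meant to end follow-up. Section 2.5 is headed as being about discontinuing the intervention. Its data sentence aims at keeping data in the analysis and cancels no visit. The 3- and 6-month ratings are scheduled for everyone. Refusal of both visits cannot be established until about month 6, so for that criterion drop-out looks more like a status label than a moment when recording stops. SAP 5.1.4 plans mITT subgroups with fewer than 30, 36, 42 or 48 qualified exercise days. The SAP 7 variable list puts stop reason and medication dose beside the follow-up scores. Both suggest that some such children are expected to have scores.

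This stands as evidence that practice is uncertain, and it rules out reading the text as proof that visits are cancelled. It does not remove the rule. Few qualified days is not the drop-out definition, because a child can fall below 48 days without two consecutive weeks off. A listed field need not be filled. Nothing in the text supplied says that drop-outs are still assessed, although the flow diagram (Protocol Figure 1) was not available for this review.

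It can also be said that SAP 4.2, not Protocol 2.5, makes the exclusion. That is true, and it would apply to any missing score. Protocol 2.5 matters because it would create missing scores that need not occur.

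A reader might infer that the plan leaves scores taken after a dose change or added therapy in limbo. It does not: SAP 4.2 excludes only for a missing primary outcome, so those scores are already in the primary analysis.

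**Conclusion.** The point holds as a conditional one and should be fixed. If Protocol 2.5 is followed as written, treatment events before month 3 cost the child the primary score, and the primary mITT set is selected on events after randomisation. Confidence is medium, because the documents do not show which practice was intended.

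A reader might go further and conclude that the primary result is biased, or biased in favour of Baduanjin. The documents do not support that. Direction and size depend on drop-out by arm and on how these children's outcomes differ, and neither is given.

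Loss of precision is not the main argument. At the planned 5% loss, power stays at 80.8%; it falls to 78.6% only at an assumed 10%, twice the documented rate. What is at stake is which children the primary comparison describes.

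**What to change.** Replace the last sentence of Protocol 2.5 with:

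> Children who stop or change the intervention remain in the study and are invited to the 3- and 6-month blinded assessments; the date and reason are recorded, and only withdrawal of consent to follow-up ends data collection.

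A matching sentence in SAP 4.2 and 5.1.1, that scores taken after such events are used in the primary analysis, would be clarification only.

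The cost is wording, plus attendance at visits already scheduled for every child. The statistical price is the possible dilution shown in the working. In return, the estimate applies to all randomised children, as Protocol 2.15.1 intends. The change reduces missing 3-month scores but does not settle how those still missing are handled, which is a separate question.

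Protocol 1.3 plans conduct to March 2022 and SAP 2.0 is dated October 2022. If follow-up has ended, the protocol sentence comes too late. The SAP clarification can still be made, and drop-outs should be reported by arm, reason and whether a 3-month score exists.
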